5 PROCEDURES

5.1 Study procedures. Using lay language, provide a complete description of the study procedures, including the sequence, intervention or manipulation (if any), drug dosing information (if any), use of records, time required, and setting/location. If it is available and you think it would be helpful to the IRB: Upload a study flow sheet or table to the **Supporting Documents** SmartForm in **Zipline**.

For studies comparing standards of care: It is important to accurately identify the research procedures. See UW IRB [POLICY: Risks of Harm from Standard Care](#) and the draft guidance from the federal Office of Human Research Protections, ["Guidance on Disclosing Reasonably Foreseeable Risks in Research Evaluating Standards of Care"](#); October 20, 2014.

This research study will be conducted in addition to standard of care procedures for PrEP use. Therefore, clinical procedures, including blood draws for laboratory testing, STI screening, PrEP prescriptions, and adherence counseling will be performed in accordance with the clinic's standard of care. Participants will be followed in this study and have visits at entry (baseline), and then at months 1, 3 and 6.

The research procedures, in addition to informed consent, that all participants will get in addition to the standard of care, are the following:

- Randomization: After consent has been obtained the clinical site will send documentation of eligibility (checklist) and the signed informed consent, HIPAA authorization, and ROI to the study team at UW. The site will either email the documents or provide them in person to a study team member. Once these documents are received, the research coordinator will send the participant a link to the baseline survey. After completion of the baseline survey, the participant will be randomized to one of the two intervention groups: standard of care, or peer navigation. The research coordinator will open a sequentially numbered, sealed envelope with the study allocation (generated by site using blocked randomization with variable block sizes and random number generator). They will record the treatment assignment of the participant in their de-identified chart and send a text or email to inform the participant of their assignment.

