- Surveys: Participants will be asked to complete an online survey at the entry visit (baseline) and at 3 and 6 months. They will be sent a unique link to the survey by text and reminders if they do not complete it. If a participant does not complete their baseline survey within 7 days they will be replaced in the study. Extenuating circumstances (such as sudden job loss, health emergencies and legal issues for robberies) can be made to extend this baseline survey deadline within a reasonable timeframe at the discretion of the PI.

- Fingerstick for dried blood spots: At all follow-up visits (1 month, 3 months, and 6 months) we will collect a blood specimen via fingerstick and use it to obtain dried blood spots, which will be used to test for the presence of the medications in PrEP (tenofovir and emtricitabine).
- Intervention groups:
 - Standard of care: The up to 20 participants who are assigned to the standard of care, will only be asked to participate in the research procedures described above.
 - Peer navigation: For the up to 20 participants who are assigned to the peer navigation group, they will receive peer support. These activities include, but are not limited to, in-person meetings, appointment reminders and escort, refill assistance, and check-ins about adherence. The activities that the participant receives will be in response to their needs and requests. The peer will introduce themselves to participants in this intervention arm within 2 business days of when the participant completes the survey, via their preferred method of contact (as recorded at the clinic during the entry visit). The peer will schedule their first in-person meeting within 1 week of enrollment. As some meth users will have greater functioning than others, the peer will create an individualized plan for each subject and tailor activities and resources based on acuity. Individualized plans will be completed at study enrollment and exit to be able to record needs and progress during the study. Additional individualized plans may be completed during follow-up at the discretion of the peer and depending on the needs and acuity of the participant.

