¹ The research procedures of the enrollment visit may be performed on the same day of the initial PrEP clinical visit, or on the following day.

New activities for all MSM/TGP participants and PrEP providers:

The research coordinator will conduct semi-structured interviews with all willing study MSM/TGP participants and PrEP provider (prescribers, caseworkers, peer educators, and PrEP navigators) participants to better understand the challenges and barriers to PrEP initiation and engagement in the PrEP care continuum. Interviews will be digitally audio-recorded and transcribed verbatim, and identifying information will be deleted. The information sheet and interview guide for these interviews have been uploaded to Zipline. Interviews can be conducted in-person, by phone, or by Zoom videoconference.

Note: Remote interviews will be preferred, however an in-person option is being made available due to potential access issues. It is anticipated that most (if not all) will be remote. Attention will be paid to COVID safety protocols and guidelines including symptom screening if an interview is done in-person.

5.2 Data variables. Describe the specific data you will obtain (including a description of the most sensitive items). If you would prefer, you may upload a list of the data variables to the **Supporting Documents** SmartForm instead of describing the variables below.

We will obtain contact information from the clinic at enrollment and all participants will complete an ROI so we can obtain their clinical information related to PrEP. We will also obtain drug level testing results (tenofovir and emtricitabine) once the study is over.

The data we will obtain from the baseline and follow-up surveys are uploaded in Supporting Documents.

The peer will complete individualized plans for each participant assigned to peer navigation. The peer will also complete a contact log with all of the participant contacts they have that are not already recorded in the text platform, individualized plans, or the peer's cell phone. Examples of the individualized plan and contact log have been uploaded in the Supporting Documents SmartForm.

We will obtain interview data from participants who consent to participate in an end-of-study interview. An interview guide has been uploaded in the Supporting Documents SmartForm with interview questions.

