PHI is individually-identifiable healthcare record information or clinical specimens from an organization considered a "covered entity" by federal HIPAA regulations, in any form or media, whether electronic, paper, or oral. If you will use UW Medical Records, you must answer yes to this question.

	No
	Yes

No → If no, skip the rest of this question; go to [question 5.8](#)

Yes → If yes, answer all of the questions below.

a. Describe the PHI you will access or obtain, and the reason for obtaining it. *Be specific.*

We will obtain the health information that is in the clinical charts at the study sites where participants are enrolled that is relevant to PrEP follow-up. All participants will sign a HIPAA Authorization and an ROI at study entry. This data will include appointment dates, behavioral eligibility for PrEP, any reported side effects from PrEP, prescription orders and refills, reported PrEP adherence, any discontinuation of PrEP and reason, and other information that may be recorded regarding their PrEP use and follow-up.

b. Is any of the PHI located in Washington State?

	No
	Yes

c. Describe how you will access or obtain the PHI. *Be specific.*

At study entry, all participants will sign a HIPAA Authorization and an ROI between the clinic site and the UW study team to share PrEP-related clinical records.

d. For which PHI will you obtain HIPAA authorization from the subjects by having them sign a HIPAA Authorization form, before obtaining and using the PHI?

We will ask participants to authorize us to access their PrEP-related medical records using both a HIPAA Authorization and an ROI prior to obtaining any PHI.

Confirm by checking the box that you will use the UW Medicine [HIPAA Authorization](#) form maintained on the HSD website if you will access, obtain, use, or disclose UW Medicine PHI.

	Confirmed
-------------------------------------	-----------

e. For which PHI will you NOT obtain HIPAA authorization from the subjects?

None.

Provide the following assurances by checking the boxes.

The PHI will not be reused or disclosed to any other person or entity, except as required by law, for authorized oversight of the research study, or for other research for which the use or disclosure of PHI would be permitted.

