In order to obtain consent, the clinical/study staff will meet with an interested and eligible participant in a private setting and review the UW HSD-approved consent form with them. If the staff has a time conflict or are at a site outside of Gay City or Kelley-Ross the clinic staff will reach out to the UW study team (Principal Investigator, Study Coordinator and/or Peer Navigator) to provide consent. In these cases one of the UW study team members will consent the individual within 7 days at either at the study site or in another private location at UW or with a community partner (e.g., a private room at Gay City). All personnel who perform consent will ensure that the participant knows that participating in research is voluntary and that they can stop their participation at any time. Specifically, the clinical/study staff will inform the individual that they can receive PrEP at the clinic without participating in the study, if they would prefer not to participate. Once the consent is reviewed, all questions have been answered, and the staff is confident the client understands the procedures, the client and the staff will both sign and date the consent form.

The Gay City PrEP clinic also offers PrEP visits by telemedicine for people who cannot come to the Wellness Center during the weekly clinic hours and at outreach settings where Gay City offers HIV testing, including UTOPIA in Kent, WA. Telemedicine visits are only done for the initial PrEP visit for clients; for follow-up PrEP visits the HIV tester will see the client without the provider's presence via telemedicine. During the initial visit the HIV tester is with the client in-person and uses a HIPAA-compliant telemedicine platform (Zoom) through their UW Net ID account to connect with the provider. Together, the tester and provider conduct the visit, including informing the client about PrEP, assessing for eligibility, and determining next steps (e.g., how to help client with insurance/financial assistance for PrEP; if behaviorally eligible, provider will prescribe PrEP once eligibility is confirmed after reviewing lab results). The tester performs any specimen collection, weight measurements, etc. The tester and provider are in private settings during telemedicine appointments to ensure the privacy of the client.

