In response to the study sponsor's request we have formed a DSMB for this study. The DSMB will meet prior to the start of the study to review the protocol and annually until study completion. The Data Safety and Monitoring Plan (DSMP) that is uploaded to the Supporting Document SmartForm supersedes the DSMP that was originally proposed in the Funding Application.

10.6 Un-blinding. If this is a double-blinded or single-blinded study in which the participant and/or you do not know the group to which the participant is assigned: describe the circumstances under which un-blinding would be necessary, and to whom the un-blinded information would be provided.

10.7 Withdrawal of participants. If applicable, describe the anticipated circumstances under which participants will be withdrawn from the research without their consent. Also, describe any procedures for orderly withdrawal of a participant, regardless of the reason, including whether it will involve partial withdrawal from procedures and any intervention but continued data collection or long-term follow-up.

While the study team will do their best to retain all participants for the duration of the study, it is possible that participants will discontinue their participation early, before the final 6-month visit. This could occur due to participant choice, study team decision, or experiencing an adverse event (AE). If someone has an AE related to PrEP and is willing to remain in the study, we will discontinue PrEP in that participant, but continue to follow them to monitor the AE and its resolution. If someone exits the study early, we will attempt to schedule a final visit that will include the same procedures as a scheduled month 3 or 6 visit. If a participant refuses to return for a final visit, we will ask them to at least complete an exit CASI. Reasons for early discontinuation will be recorded on study data collection forms.

In addition, the study team will discontinue participants if they do not complete a baseline CASI within 7 days (with the exception of extenuating circumstances) of their entry visit, in which case they will be replaced. If the study team thinks that the participation of a study participant could cause harm to them or the study

staff (e.g., inappropriate, aggressive behavior), the study team may end participation for that participant early. We do not expect this to occur.

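### Does the same-or-next-day enrollment footnote clash with the 7-day consent and survey allowances badly enough to need a change?

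*Protocol*

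**What the plan says.** Three places in the Protocol bear on when a participant is enrolled.

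- **Section 5.1, schedule table and footnote 1.** The Enrollment column lists research consent and the online survey among the research procedures. The footnote says these "may be performed on the same day of the initial PrEP clinical visit, or on the following day".
- **Section 8.2b.** If staff have a time conflict, or the site is neither Gay City nor Kelley-Ross, then "one of the UW study team members will consent the individual within 7 days". The start of the 7 days is not given.
- **Sections 5.1 and 10.7, survey deadline.** Section 5.1: "If a participant does not complete their baseline survey within 7 days they will be replaced in the study". Section 10.7 discontinues and replaces participants who "do not complete a baseline CASI within 7 days (with the exception of extenuating circumstances) of their entry visit". Section 5.1 lets the principal investigator extend the deadline in extenuating circumstances.

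The order of events is fixed in section 5.1. The site sends the signed consent and authorization forms to the study team. "Once these documents are received, the research coordinator will send the participant a link to the baseline survey". Randomization follows completion of that survey.

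Section 5.1 twice equates entry with baseline. It also has the participant's preferred contact method "as recorded at the clinic during the entry visit". Section 5.7c adds: "At study entry, all participants will sign a HIPAA Authorization and an ROI between the clinic site and the UW study team". For the navigation arm, the peer's introduction is due "within 2 business days of when the participant completes the survey", and the first meeting is to be scheduled within a week of enrollment.

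**The concern.** Read literally, the footnote allows two calendar days for consent while section 8.2b allows up to a week, so a consent on day 5 complies with one and breaches the other. The 7-day replacement rule is also hard to date on the late-consent route, because the entry visit could be the PrEP visit or the later consent contact. The peer targets appear to start from two different events, so a late survey might use up the week allowed for the first meeting before the arm is known.

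The stake is the feasibility result. Section 1.5 makes acceptability and feasibility the purpose of the pilot, so who is enrolled, replaced or contacted on time is part of what will be reported. If two coordinators classified the same late-consent participant differently, enrollment and replacement counts would depend on who did the counting.

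**Working it through.** No sample size, power or event figure is involved. The check sets the stated windows side by side, in days from the initial PrEP visit (day 0). It assumes that the 7 days in section 8.2b run from that visit; the Protocol does not say so.

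**1. Consent window.**
- Footnote 1: days 0 to 1.
- Section 8.2b: days 0 to 7, on the exception route only.
- Outside the footnote but inside 8.2b: days 2 to 7.

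Consent on day 0 or 1 meets both. The 7-day figures are upper limits, so the conflict is confined to the later part of the exception route.

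**2. Survey deadline, with consent on day c.**
- Reading A, entry is the PrEP visit: the deadline is day 7, so days left = 7 − c. For c = 2, 5, 7 this gives 5, 2, 0.
- Reading B, entry is the consent contact: the deadline is day c + 7. For c = 7 this is day 14.
- The readings differ by (c + 7) − 7 = c days: at most 1 day on the ordinary route (c = 0 or 1), and at most 7 on the exception route.

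Reading A with c = 7 would replace a person who does not finish the survey on the day of consent, although the link is sent only once the signed documents have been received. Section 5.7c places the authorization forms, which travel with the signed consent, at study entry. Both facts favor Reading B. The contact details recorded at the clinic do not contradict it: on the ordinary route the PrEP visit and the consent contact are the same day or adjacent days.

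**3. Survey against footnote.** The footnote is permissive. Section 10.1 says the surveys are completed online and away from the clinic, and section 5.1 provides for reminders. Seven days therefore reads as a completion deadline for a procedure nominally assigned to the enrollment visit.

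**4. Peer targets.** Two business days are 2 to 4 calendar days (4 if a weekend intervenes; public holidays ignored).
- If enrollment means consent, counted here as day 0, a survey on day s gives an introduction deadline of s + 2 to s + 4. For s = 3 this is 5 to 7; s = 4, 6 to 8; s = 5, 7 to 9; s = 6, 8 to 10; s = 7, 9 to 11. Surveys on day 6 or 7 would always overrun the 7-day meeting target.
- The same paragraph of section 5.1 says the peer's individualized plan is completed at study enrollment. Only the navigation arm has such plans, so enrollment there cannot sensibly precede randomization. Counting from randomization, and taking it to occur on the day of the survey, the introduction is due by day 2 to 4 and the meeting is to be scheduled by day 7. The two targets are compatible.

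**5. Consequences.**
- Replacement for a missed baseline survey comes before the allocation envelope is opened, so no randomized participant is removed.
- With a 30-day month, day-7 consent puts month 1 at day 30 (Reading A) or day 37 (Reading B). The Protocol states no visit windows for months 1, 3 and 6, so neither date is out of window.
- Section 4.1 already ties eligibility to the visit at which PrEP is started, so a later consent does not reopen the criterion on recent PrEP use.

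**The case for a change.** The best case for a change is that the exception route may not be rare. Section 3.1 opens recruitment to other PrEP providers across King County because the two original sites saw very few eligible people, and the 7-day consent route applies at every added site. The footnote thus disagrees with the route added to rescue enrollment. With a planned maximum of 20 + 20 = 40, one inconsistently replaced participant is 1/40 = 2.5% of target enrollment. The baseline gloss does not settle the date either, since the baseline survey is the thing being timed.

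Two parts of this stand: footnote 1 was not aligned with section 8.2b, and no passage gives the entry visit a calendar date for late consent. The step from there to unreliable feasibility results does not stand. Consent is needed before the survey link can be sent, so a coordinator has a natural starting date in front of them. The 2.5% shows the weight of one case; it is not evidence that such cases will be misclassified. A person replaced at this stage has not been randomized and affects only pre-randomization counts.

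**Conclusion.** No change to the plan follows. One wording inconsistency is genuine: on the exception route, consent on days 2 to 7 is allowed by section 8.2b and falls outside footnote 1. One date is left open: the entry visit in section 10.7, where the readings differ by at most 1 day on the ordinary route and at most 7 on the exception route. Both are clerical. The order of consent, survey and randomization is clear, the forms signed at study entry point to the consent contact as the anchor, and the investigator has discretion over the survey deadline in extenuating circumstances.

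The peer-contact overrun disappears once enrollment is read consistently with the arm-specific plans in the same paragraph. Randomization, arm balance and the stated numbers are untouched.

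This rests on two assumptions: that the 7 days in section 8.2b run from the PrEP visit, and that staff apply one entry date throughout. If they did not, the effect would be limited to pre-randomization enrollment and replacement counts and to shifts of up to 7 days in nominal follow-up dates.

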6.1 Involvement of minors. Does your research include minors (children)?

Minor or child means someone who has not yet attained the legal age for consent for the research procedures, as described in the applicable laws of the jurisdiction in which the research will be conducted. This may or may not be the same as the definition used by funding agencies such as the National Institutes of Health.

- In Washington State the generic age of consent is 18, meaning that anyone under the age of 18 is considered a child.
- There are some procedures for which the age of consent is much lower in Washington State.
- The generic age of consent may be different in other states, and in other countries.

	No	→ If no, go to Section 8 .
	Yes	→ If yes, provide the age range of the minor subjects for this study and the legal age for consent in your population(s). If there is more than one answer, explain.

	Don't know	→ This means is it not possible to know the age of your subjects. For example, this may be true for some research involving social media, the Internet, or a dataset that you obtain from another researcher or from a government agency. Go to Section 8 .
--------------------------	-------------------	---

6.2 Parental permission. **Parental permission** means actively obtaining the permission of the parents. This is not the same as "passive" or "opt out" permission where it is assumed that parents are allowing their children to participate because they have been provided with information about the research and have not objected or returned a form indicating they don't want their children to participate.

a. Will you obtain parental permission for:

	All of your research procedures	→ Go to question 6.2b .
	None of your research procedures	→ Use the table below to provide your justification, and skip question 6.2b.

Some of your research procedures

→ Use the table below to identify the procedures for which you will not obtain written parental permission.

Be sure to consider all research procedures and plans, including screening, future contact, and sharing/banking of data and specimens for future work.

Children Group ¹	Describe the procedures or data/specimen collection (if any) for which there will be NO parental permission ²	Reason why you will not obtain parental permission	Will you inform them about the research? ³	
			YES	NO
				
				
				
				
				
				

Table footnotes

1. If your answer is the same for all children groups or all procedures, you can collapse your answer across the groups and/or procedures.
2. If you plan to obtain identifiable information or biospecimens without parent permission, any waiver granted by the IRB does not override parents' refusal to provide broad consent (for example, through the Northwest Biobank).
3. Will you inform them about the research beforehand even though you are not obtaining active permission?

b. Indicate by checking the appropriate box(es) your plan for obtaining parental permission

Both parents, unless one parent is deceased, unknown, incompetent, or not reasonably available; or when only one parent has legal responsibility for the care and custody of the child

One parent, even if the other parent is alive, known, competent, reasonably available, and shares legal responsibility for the care and custody of the child.

This is all that is required for minimal risk research.

If you checked both boxes, explain:

6.3 Children who are wards. Will any of the children be wards of the State or any other agency, institution, or entity?

No

